2.4. Definition of Subgroups

The following subgroups will be investigated for safety: pre-existing neutralizing antibody response against the Ad26 vector at baseline, i.e., baseline titers \geq the lower limit of quantification (LLOQ) versus baseline titers below the LLOQ.

3. DATA REVIEW COMMITTEE REVIEW

An internal data review committee (DRC) will be commissioned for this study, comprised of sponsor personnel not directly involved in the conduct of the study, who have expertise in clinical study conduct and vaccines. There is one planned DRC meeting when the final participant in the initial safety cohort (Cohort 1) had his/her Day 8 visit. The DRC will review all safety data collected up to that point and provide their recommendation regarding the continuation of the study. The DRC will also convene to discuss any significant or unexpected safety issues. The investigator and SRP/SRS will inform the DRC of any AE of concern. If deemed necessary for safety review, the DRC may request the randomization codes and review unblinded data, if applicable. Moreover, the DRC may review unblinded immunogenicity data during the course of the study if this is deemed necessary for future vaccine development-related decisions. If this is the case, a biomarker representative (not involved in the conduct of the study) will be part of the DRC. Further information regarding the role of the DRC are included in the DRC Charter. Finally, in case additional analyses are requested this SAP will also serve as a guidance.

4. SUBJECT INFORMATION

Subject information will be shown for the full analysis set.

4.1. Demographics and Baseline Characteristics

Demographic characteristics and screening/baseline characteristics will be tabulated and summarized with descriptive statistics per vaccine regimen and over all subjects.

The following demographic and baseline characteristics will be summarized.

- Sex (Female/Male)
- Age (years)

- Race
- Ethnicity
- Height (cm)
- Weight (kg)
- BMI (kg/m²)

4.2. Disposition Information

The number and percentage of subjects screened, subjects in the FA, in the PPI, subjects vaccinated and not randomized, subjects randomized and not vaccinated and discontinued subjects (study discontinuation and vaccination discontinuation) with the reason of discontinuation will be tabulated per vaccine group and overall.

The number of subjects and percentage per phase will also be tabulated.

4.3. Protocol Deviations

Major protocol deviations will be summarized.

4.4. Concomitant Medications

The analysis of concomitant therapies will be done using the WHO drug coded terms.

Based on their start and stop date, concomitant therapies will be reported in each applicable phase.

If a concomitant therapy record missed components of its start and/or stop dates (time, day and/or month and/or year):

- In case of partial start or stop dates, the concomitant therapy records will be allocated to periods using the available partial information, without imputations. If, for example, only month and year are available, these will be compared to the month and the year of the periods, and the concomitant therapy record will be allocated to the period(s) where these date parts match. This rule may lead to assignment to multiple periods. The same rule applies for identifying whether a concomitant therapy was administered during 8 days following a vaccination. For example, if the vaccination was administered on 30 December 2017 and the concomitant therapy start date is January 2018, then the concomitant therapy will be assumed to have started within 8 days of the vaccination.
- In case of a completely missing start date, the concomitant therapy will be considered as having started before the trial.
- In case of a completely missing end date, the concomitant therapy will be considered as ongoing at the end of the trial.

There will be special attention to any systemic use of analgesics/antipyretics that started during 8 days following each vaccination (00:00 of day of vaccination + 7 days). The following ATC/DD codes will be used for this: N02A (OPIOIDS) and N02B (OTHER ANALGESICS AND ANTIPYRETICS), M01A (ANTIINFLAMMATORY AND ANTIRHEUMATIC PRODUCTS, NON-STEROIDS) and M01B (ANTIINFLAMMATORY/ANTIRHEUMATIC AGENTS IN

COMBINATION) (ATC/DD Index). The classes will be added in a footnote in all related tables and listings. For the use of analgesics/antipyretics which are taken on the day of vaccination, an exception is made in case the time is before vaccination. In this case, the concomitant medication is also allocated to the post-dose period.

Concomitant therapies will be tabulated per period.

5. SAFETY

Safety analyses will be performed on the FA set. Continuous variables will be summarized using the following statistics, as appropriate: number of observations, median, quartiles (Q1 and Q3), minimum and maximum. Frequencies and percentages (one decimal place) will be generated for categorical variables. No formal comparisons between groups will be provided.

One type of safety tables will be shown. The by regimen layout, safety data will be analysed by vaccine regimens as designed per protocol and data will be presented by period. Denominator for the percentages is the number of subjects with considered data in the considered population and period for a certain regimen (incidence per 100 subjects/period).

5.1. Adverse Events (AE)

5.1.1. Definitions

Solicited AEs shown in the tables and listings will be extracted from the SDTM CE domain which will be based on the diary pages and onsite assessment pages of the CRF ([ATTACHMENT 2](#)). When participants are given two injections in opposite arms at a given visit, then local solicited AEs will be collected and reported for both arms separately. For unsolicited AEs, only AEs with start date (grade and/or relation) within the 28-day period following vaccination will be presented in the safety tables except for SAEs, which will be captured and tabulated in the outputs covering the whole study period. All other unsolicited adverse events collected outside this 28-day period will be presented through listings. Any RTI recorded as an AE in the eCRF will be excluded from any AE analysis if the central laboratory RT-PCR is subsequently found to be positive for RSV.

Solicited local AEs will be by definition considered as related to the study vaccine.

The severity of the AEs will be classified as grade 1 to 4. Solicited events that are graded less than grade 1, are not considered as AE.

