10.2. Discontinuation of Study Vaccine/Withdrawal from the Study

Discontinuation of Any Study Vaccine

A participant will not be automatically withdrawn from the study if he or she has to discontinue from study vaccination before the end of the study vaccine regimen.

Participants will be discontinued from vaccination for the reasons listed below. These participants must not receive any additional dose of any study vaccine but should continue to be monitored for safety and, if this does not result in safety risks for the participant, for immunogenicity (if the reason for discontinuation is not because of impaired functioning of the immune system) and/or other study procedures (eg, RTI follow-up). Additional unscheduled visits may be performed for safety/reactogenicity reasons, if needed.

In the event of questions, the investigator is encouraged to contact the sponsor:

- Anaphylactic reaction post vaccination, not attributable to causes other than vaccination
- An SAE or other potentially life-threatening (Grade 4) event that is determined to be related to study vaccine
- Any related AE, worsening of health status or intercurrent illness that, in the opinion of the investigator, requires study vaccine discontinuation
- Chronic or recurrent use of immunosuppressants (after discussion with the sponsor)
- Unblinding on the participant level that, in the opinion of the sponsor, would compromise the integrity of the data

Participants who miss a vaccination, not due to the reasons above, can receive subsequent vaccinations if, at the time of administration, the investigator determines that they are eligible to receive the vaccination according to the criteria in Section 10.3. In the event of questions, the investigator is encouraged to contact the sponsor.

Withdrawal from the Study

Each participant has the right to withdraw from the study at any time for any reason without affecting the right to treatment by the investigator. The investigator should make an attempt to contact participants who did not return for scheduled visits or follow-up. Although participants are

not obliged to give a reason for withdrawing prematurely, the investigator should make a reasonable effort to ascertain the reason(s) while fully respecting the participant's rights.

A participant will be withdrawn from the study for any of the following reasons:

- Lost to follow-up
- Withdrawal of consent
- Death
- Repeated failure to comply with protocol requirements

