12.3. Procedures

12.3.1. All Adverse Events

All AEs and special reporting situations, whether serious or non-serious, that are related to study-related procedures or that are related to non-investigational (concomitant) Janssen products will be reported from the time a signed and dated ICF is obtained onwards.

All other AEs and special reporting situations will be reported until 28 days (including relevant visit window, if applicable) after first dose of vaccine and thereafter, pre-dose on the vaccination day, and for 28 days (including relevant visit window, if applicable) following each subsequent vaccination. Unsolicited AEs with the onset date outside the time frame defined above (>28 days after previous vaccination), which are ongoing on the day of the subsequent vaccination, should be recorded on the eCRF AE page.

All SAEs and AEs leading to discontinuation from the study/vaccination (regardless of the causal relationship) are to be reported from the moment of first vaccination until completion of the participant's last study-related procedure, which may include contact for safety follow-up.

Clinically relevant medical events occurring between ICF signature and date of first vaccination will be collected on the Medical History eCRF page as pre-existing conditions.

Solicited AEs will be recorded by each participant in the participant diary for 7 days after each vaccination. The investigator will review each participant's diary at the subsequent in-clinic visit and discuss the information from the diary with the participant. The diary information will be transcribed by the study-site personnel in the diary forms in the eCRF.

The sponsor will evaluate any safety information that is spontaneously reported by an investigator beyond the time frame specified in the protocol.

The investigator will monitor and check the study data, including all AE and clinical laboratory data, as they become available and will make determinations regarding the severity of the adverse experiences and their relation to vaccine. All AEs will be deemed related to vaccine or not related to vaccine, according to Section 12.1.2.

The investigator must review both post-injection reactogenicity and other AEs to insure the prompt and complete identification of all events that require expedited reporting as SAEs, invoke pausing rules or are other serious and unexpected events.

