2. GENERAL ANALYSIS DEFINITIONS

2.1. Study phases

A baseline (or reference) value will be defined as the value of the last available assessment prior to the first vaccination on Day 1.

The safety analysis will present all results by period, except the serious adverse events (SAE) that will be presented by phase and period (See Section 0). Immunogenicity results will be presented per scheduled time point as appropriate. Listings will be shown per phase and time point.

Study day or relative day is defined as follows:

Study Day = visit date - date of Day 1 + 1; if visit date \geq date of Day 1 (date of first vaccination).

Study Day = visit date - date of Day 1; if visit date $<$ date of Day 1 (date of first vaccination).

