2.1.1. Phase definitions

The phases in the study will be constructed as follows for all groups:

Table 1: Phase Definitions of Cohort 1, 2 and 3

Phase	Phase number	Period	Period number	Interval	
				From	To
Screening	1			00:00 of the date of signing the informed consent form ^a	One minute prior to Dose 1 on Day 1
Regimen	2	Post-Dose 1	1	Date and time of Dose 1 (Day 1)	Minimum of: 
 a) 23:59 at the date of database cut-off b) Maximum (28 days after first vaccination at 23:59, scheduled visit 4 weeks after first vaccination at 23:59) c) 23:59 at the date of last contact (for early discontinuation of the study)
Follow-Up 1	3			1 minute after end of Post-Dose 1 period	Minimum of: 
 a) 23:59 at the date of database cut-off b) One minute prior to date and time of the next vaccination c) 23:59 at the date of last contact (for completed and early discontinuation of the study)

Table 1: Phase Definitions of Cohort 1, 2 and 3

Phase	Phase number	Period	Period number	Interval	
				From	To
Regimen	2	Post-Dose 2	2	Date and time of Dose 2 (Day 57)	Minimum of: a) 23:59 at the date of database cut-off b) Maximum (28 days after second vaccination at 23.59, scheduled visit 4 weeks after second vaccination at 23:59) c) 23:59 at the date of last contact (for early discontinuation of the study)
Follow-Up 2	4			1 minute after end of Post-Dose 2 period	Minimum of: a) 23:59 at the date of database cut-off b) One minute prior to date and time of the next vaccination c) 23:59 at the date of last contact (for completed and early discontinuation of the study)
Regimen	2	Post-Boost (Month 12)	3	Date and time of Month 12 Boost	Minimum of: a) 23:59 at the date of database cut-off b) Maximum (28 days after the Month 12 boost vaccination at 23.59, scheduled visit 4 weeks after the Month 12 boost vaccination at 23:59) c) 23:59 at the date of last contact (for early discontinuation of the study)
Follow-Up Boost (Month 12)	5			1 minute after end of Post-Boost (Month 12) period	Minimum of: a) 23:59 at the date of database cut-off b) One minute prior to date and time of the next vaccination c) 23:59 at the date of last contact (for completed and early discontinuation of the study)

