5.1.2. Analysis of Adverse Events

Number and percentage of subjects with at least one particular AE (unsolicited/solicited) will be tabulated. Unsolicited AEs will be summarized by System Organ Class and Preferred Term. Solicited AEs will be summarized by class (local, systemic) and preferred term.

For solicited AEs following tables will be provided: summary, by worst severity grade, grade 3, related (systemic only), time to onset (in days) and duration (in days) for most frequent events and body temperature. Note: Duration is defined as number of days from the start of the event until

resolution of the event. The time to first onset is defined as (date of first onset – reference date + 1). The reference date is the start date of the regimen period.

For unsolicited AEs following tables will be provided: summary table (including SAE, fatal outcome and discontinuation), all events, most frequent events, grade 3 events, events leading to permanent stop of vaccine, related events and SAEs. Potential adverse events of special interest (AESI) will be tabulated.

A summary of the solicited and unsolicited AEs will also be tabulated by subgroups of pre-existing Ad26 neutralizing antibody (<LLOQ, >=LLOQ). Refer to the subgroup definition in Section 2.4.

Listings and/or subject narratives will be provided as appropriate, for those subjects who die, discontinue study vaccinations due to an AE, or experience a severe or serious AE.

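### The table of AEs leading to permanent stop of vaccine, and the discontinuation row of the AE summary, omit non-serious AEs that start after the 28-day window, although the protocol collects these AEs throughout the study

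*SAP*

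**What the plan says.** **Tabulation.** SAP 5.1.1 states that "only AEs with start date (grade and/or relation) within the 28-day period following vaccination will be presented in the safety tables except for SAEs", and sends the remainder elsewhere: "All other unsolicited adverse events collected outside this 28-day period will be presented through listings". SAP 2.1 agrees: "The safety analysis will present all results by period, except the serious adverse events (SAE) that will be presented by phase and period". SAP 2.1.1 ends a post-dose period, absent a data cut-off or early discontinuation, at "Maximum (28 days after first vaccination at 23:59, scheduled visit 4 weeks after first vaccination at 23:59", with the same form after later doses. What follows belongs to a follow-up phase.

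**Tables planned.** SAP 5.1.2 lists a summary table with a discontinuation entry, and tables that include "events leading to permanent stop of vaccine, related events and SAEs". Neither the discontinuation entry nor the permanent-stop table is released from the 5.1.1 rule.

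**Collection.** Protocol 12.3.1 treats SAEs and AEs leading to discontinuation as a pair: "All SAEs and AEs leading to discontinuation from the study/vaccination (regardless of the causal relationship) are to be reported from the moment of first vaccination", up to the participant's last study-related procedure. The Synopsis and section 3.1.2 say the same. Protocol 10.2 includes among the reasons to stop vaccination: "Any related AE, worsening of health status or intercurrent illness that, in the opinion of the investigator, requires study vaccine discontinuation". It sets no time limit and does not require the event to be serious.

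**Disposition.** SAP 4.2 tabulates study and vaccination discontinuations with their reasons.

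**The concern.** The protocol collects two kinds of event over the whole study. The SAP tabulates one of them, SAEs, over the whole study and confines the other to the post-dose windows. A table titled by its outcome, permanent stop of vaccine, is thus filtered on a criterion unrelated to that outcome.

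Take a Cohort 3 participant whose non-serious AE starts on Day 200 and ends vaccination before the Month 12 dose. Disposition counts a vaccination discontinuation, with AE as the reason if so recorded. The AE table that should name the event does not contain it. Cohort 3 is there to assess the safety of a regimen with Month 12 and Month 24 boosters, so a reader will look to that table to see how often AEs prevented revaccination, and by which term. The figure would be too low whenever such events occur, and the two tables would disagree without explanation.

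**Working it through.** The documents state no figure on this point, so there is none to reproduce. The check is a comparison of text followed by a day count.

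**Which events fall out.** An AE is missing from the permanent-stop table if it meets all three conditions:
1. It is not serious (SAEs are exempt under SAP 5.1.1).
2. It starts after the post-dose period. The cut is on start date, so an AE starting on Day 20 that later cancels the Month 12 dose stays in, and one starting on Day 200 does not.
3. It leads to permanent stop of vaccine.

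For the discontinuation row, condition 3 also covers AEs leading to study discontinuation. A potential AESI meeting these conditions is tabulated beyond 28 days under SAP 5.1.3, but in a separate table.

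**How much time is uncovered.** Inputs are the scheduled dose days (protocol Tables 12 to 14), the 28-day window (SAP 5.1.1) and its extension to the four-week visit (SAP 2.1.1). An AE can stop a later dose only between the first and last scheduled doses, so

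- T = day of last dose − day of first dose
- inside = window length × number of doses before the last
- outside = T − inside

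| Design | Dose days | T | Inside | Outside | Share |
|---|---|---|---|---|---|
| Cohort 3 one-dose | 1, 365, 730 | 729 | 2 × 28 = 56 | 673 | 92.3% |
| Cohort 1 | 1, 57, 365 | 364 | 2 × 28 = 56 | 308 | 84.6% |
| Cohort 2 | 1, 57 | 56 | 28 | 28 | 50.0% |

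The result barely depends on the visit extension. With the four-week visit at its +3-day limit (31 days), the outside shares are 667/729 = 91.5%, 302/364 = 83.0% and 25/56 = 44.6%. The visit after the Day 57 dose may be up to 10 days late; in Cohort 1 that gives 31 + 38 = 69 days inside and 295/364 = 81.0% outside. Giving the Cohort 3 Month 12 dose early within its window leaves 673 of 729 unchanged.

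**Groups 14 and 15, long-term phase.** Their last scheduled injection is Day 57 and the added visits are Days 912 and 1095. No dose remains to be stopped, so the permanent-stop table is unaffected. AEs leading to discontinuation are still collected there, and non-serious ones would be missing from the discontinuation row.

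**The case against.** The strongest reply is that the SAP follows the protocol's own analysis section. Protocol 11.5 includes AEs with onset up to 28 days after vaccination and all SAEs, which is the same rule; section 12.3.1 governs reporting, and collecting an event does not oblige anyone to tabulate it. This stands. A reader might infer that the SAP departs from the protocol's planned analysis; it does not. The gap is between the collection rule and the tabulation rule. Protocol 11.5 also allows summaries for participants who discontinue vaccine due to an AE, without naming a window, so the fix is compatible with it.

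Second, the events are not lost. They are listed under SAP 5.1.1, SAP 5.1.2 foresees listings or narratives as appropriate for participants who stop vaccination due to an AE, and disposition counts them by reason. This also stands, and it limits the harm. But a listing gives no frequency by group and term, which is what the planned table is for.

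Third, AEs leading to discontinuation are not a Cohort 3 primary endpoint: those are SAEs to study end, solicited AEs for 7 days and unsolicited AEs for 28 days. True. The point concerns a table the SAP chose to plan, not an endpoint definition.

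Fourth, the affected set (non-serious, late-starting, vaccine-stopping) may be very small. The documents cannot settle this either way.

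**Conclusion.** The point holds on the plain text: as written, the permanent-stop table and the discontinuation row undercount their own subject and will not reconcile with disposition if any such event occurs.

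Its size can be given only as time at risk: 92% of the days between first and last scheduled dose in Cohort 3 one-dose, 85% in Cohort 1 and 50% in Cohort 2 fall outside the table windows. It is tempting to read these as the proportion of vaccine-stopping AEs that would be missed. The documents do not support that. They give no rate for such events, AEs may cluster after doses, and late events that are SAEs are tabulated anyway. The undercount could be anything from none upward.

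Two other inferences also go too far. It is not true that every late non-serious AE is kept out of all tables, because potential AESIs have their own. And the permanent-stop table is not affected in the Groups 14 and 15 long-term phase.

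The conclusion assumes that the 5.1.1 rule applies to the 5.1.2 tables, since no exemption is stated, and that doses fall on their scheduled days.

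**What to change.** - **SAP 5.1.1:** extend the exception from SAEs to SAEs and AEs leading to discontinuation of study vaccine or of the study, tabulated over the whole study.
- **SAP 2.1:** allow the permanent-stop table and the discontinuation row to be shown by phase as well as by period, so that follow-up phases appear. The by-period layout and denominators in SAP section 5 need a matching line.
- **Protocol 11.5 and 12.1.1:** align with 12.3.1. Section 11.5 should name AEs leading to discontinuation beside SAEs. Section 12.1.1 limits other non-serious AEs to 28 days and only cross-refers to 12.3.1 for the time of last recording, without restating the exception; footnote m to the Schedule of Activities has the same limit and should be brought into line.

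The data are already to be collected, so the cost is a changed filter on one table and one summary row, plus the wording above. The only downside is that the count can rise, giving a slightly less favourable table.
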